6.2. Safety Assessments

Safety assessments for all patients will include medical history, physical and neurological examinations, vital signs (seated or supine blood pressure [depending on patient age and ability], seated blood pressure, pulse rate, temperature, and respiration rate), clinical laboratory testing (hematology, chemistry, liver enzymes, and serum bilirubin), prior medication history (assessment of past/current AETs and concomitant medications), and AE assessments. The safety assessments will be conducted for each patient at specific study Days and Visits, as indicated in [Table 1](#). In addition to the safety assessments required by the study protocol, the investigator will monitor patients as recommended in the current FDA-approved vigabatrin prescribing information.

6.2.1. Demographics and Medical History

The investigator or designee will record the following information during the Screening Period: demographic data, including sex, date of birth, race, ethnicity, medical history, medications history, and concomitant medications.

6.2.2. Physical Examinations

The first physical examination will include evaluation of general appearance, ears, eyes, nose, and throat (EENT), heart, peripheral vasculature, lungs, musculoskeletal system, abdomen, endocrine system, and skin. Height/length and weight will be obtained. Subsequent brief physical exams will consist of general appearance, height/length and weight. Head circumference will be collected.

6.2.3. Neurological Examinations

A complete neurological examination will be performed at Screening, Visit 6, Visit 9 and Early Withdrawal. This exam will include mental status, visual assessment, nystagmus, cranial nerves, motor and sensory systems, reflexes coordination and gait (if applicable based on age). A brief neurological exam will be completed at all other visits; this will not include a visual assessment. On Day 4 (Visit 3), and Day 7 (Visit 4) a brief neurological examination will be performed predose and approximately 2 hours following administration of the morning dose of the investigational product. If needed, additional visual assessments, may be performed based on the clinical recommendations for patient's treatment with vigabatrin.

6.2.4. Vital Signs

Vital signs will consist of seated or supine blood pressure (depending on patient age and ability), pulse rate, temperature, and respiration rate measurements.

Additional vital sign measurements may be performed as deemed medically necessary by research personnel.

6.2.5. Clinical Laboratory Assessments

6.2.5.1. Hematology

Blood samples for the following hematology assessments will be collected: hemoglobin, hematocrit, total and differential leukocyte count, red blood cell (RBC), and platelet count.

6.2.5.2. Chemistry

Blood samples for the following serum chemistry assessments: albumin, blood urea nitrogen (BUN), creatinine, total and direct bilirubin, alkaline phosphatase (ALP), aspartate transaminase (AST), alanine transaminase (ALT), sodium (Na⁺), potassium (K⁺), chloride (Cl⁻), lactate dehydrogenase (LDH), uric acid, glucose, and calcium.

6.2.6. Adverse Events and Serious Adverse Events

6.2.6.1. Definition of Adverse Events

An AE is defined as any untoward medical occurrence in a patient administered a pharmaceutical product during the course of a clinical investigation. An AE can therefore be any unfavorable and unintended sign, symptom, or disease temporally associated with the use of an investigational product, whether or not thought to be related to the investigational product.

Patients will be monitored throughout the study for AEs. Monitoring for treatment-emergent AEs (TEAEs) will begin as soon as the patient is dosed. All AEs must be followed until they are resolved or stabilized, or until all attempts to determine resolution of the event are exhausted. The investigator should use their discretion in ordering additional tests as necessary to monitor the progress of such events.

An AE may be:

- A new illness, not documented in the patient's medical history;
- Worsening of a concomitant illness;
- An effect of the study medication; it could be an abnormal laboratory value, as well as a significant shift from baseline within normal range which the qualified investigator or medical qualified designate considers to be clinically important;
- A combination of two or more of these factors.

Surgical procedures themselves are not AEs. They are therapeutic measures for conditions that required surgery. The condition for which the surgery is required is an AE, if it occurs or is detected during the study period. Planned surgical measures permitted by the clinical study protocol and the condition(s) leading to these measures are not AEs, if the condition(s) was (were) known before the start of study treatment. In the latter case, the condition should be reported as medical history.

Seizures or worsening seizures are not considered AEs as they are considered part of the underlying disease. Injuries that occur as a result of a seizure, such as a broken nose, and new seizure types will be considered adverse events.

Patients will be monitored throughout the study for AEs. All AEs must be followed until they are resolved or stabilized, or until all attempts to determine resolution of the event are exhausted. The investigator should use his/her discretion in ordering additional tests as necessary to monitor the progress of such events.

Adverse events reported prior to dose administration will be recorded as part of the patient's medical history.

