1.2. Nonclinical Experience

1.2.1. Safety

Nonclinical toxicological assessments of CBD conducted by Insys Development Company, Inc. thus far have concluded that 600 mg/kg/day exceeded the maximum tolerated dose in adult rats. Female rats generally appear to be more sensitive to the effects of CBD (in terms of toxicity) than similarly treated males. Because of the microscopic findings in the skin (follicular atrophy) noted in both genders at all CBD dose levels, a No Observed (Adverse) Effect Level (NOAEL) could not be determined for this study. The main GLP 6-month adult rat and 9-month cynomolgus monkey chronic toxicity studies with CBD in Medium Chain Triglycerides (MCT) are underway with few clinical signs being observed in either study.

Observations from single- and repeat-dose toxicology studies in rats and non-human primates demonstrate that CBD-induced hypoactivity is transient and does not induce psychopharmacological effects³⁷. In rats, inhalation exposure of up to 1.6 mg/kg/day of CBD (smoke) once daily for 14 days was associated with a transient dose-related hypoactivity (and prostration) and body weight gain was depressed³⁸. The target organ for toxicity was the testes (impairment of spermatogenesis and sperm maturation).

In monkeys, a single intravenous dose of CBD produced dose-related hypoactivity, sedation, and prostration.³⁶ Tremors and convulsions occurred at >150 mg/kg and mortality at ≥ 225 mg/kg (associated with respiratory arrest and cardiac failure). Liver weights were increased and testes

Weights were decreased in the 200 mg/kg groups. Whether these effects on liver and testes were test-article related could not be conclusively determined due to the small sample size. There were no other meaningful treatment-related changes in clinical signs, body weight, core body temperature, or clinical or gross anatomic pathology.

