1.2.2. Efficacy in Animal Models of Epilepsy

Plant-derived cannabidiol shows antiepileptic,⁴² antipsychotic, anti-dystonic, anti-emetic, and anti-inflammatory properties in animal models.⁴³ These models support exploring the use of cannabidiol for the treatment of epilepsy.

As an example, the anticonvulsant activity of oral cannabidiol was investigated in adult rat model of seizures (induced by maximal electroshock or audiogenic sources).⁴⁴ Cannabidiol was effective against maximal electroshock-induced seizures (median effective dose [ED₅₀] = 18 mg/kg), but only minimally effective against audiogenic-induced seizures (ED₅₀ ≥75 mg/kg). The neurotoxicity median tolerated dose (TD₅₀) was >100 mg/kg. Cannabidiol co-administered with different anti-seizure drugs (e.g., phenytoin or carbamazepine) increased or reduced their anticonvulsant activity, indicating that synergism or antagonism with cannabidiol was drug specific.

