6.2.6.4. Definition of Serious Adverse Events

A serious AE (SAE) is any AE that fulfills any of the following criteria, as per 21 CFR 312.32:

- Results in death;
- Is life-threatening;
- Requires in-patient hospitalization or prolongation of existing hospitalization;
- Results in persistent or significant disability or incapacity;
- Is a congenital anomaly or birth defect;
- Is medically significant or requires intervention to prevent one of the outcomes listed above.

Serious AEs will be captured from the time of consent through the end of the study.

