7.1. Screening Period (Visit 1)

Potential study patients will be examined before the start of the study to determine their eligibility for participation. Prior to performing any study related procedures or assessments, the Investigator will ensure that the patient's legal representative (parent[s]/caregiver[s]) provides written informed consent. Patients and their parent(s)/caregiver(s) will receive a copy of the ICF for review and must provide fully informed consent prior to study participation.

The following screening procedures and assessments are intended to be performed during Visit 1, but the patient may return to complete activities, which must be performed within 14 days of the start of the Initial Treatment Period for all patients.

- Obtain written informed consent.
- Review of inclusion and exclusion criteria (see [Sections 3.2.1](#) and [3.2.2](#)).
- Record demographic data.
- Record recent and concomitant medication and procedure history including vitamins, herbal preparations, blood products, and over-the-counter drugs. All medications taken ≤ 30 days of the Screening Visit must be documented in the concomitant medications section of the CRF.
- Record all prior and current anti-epileptic therapies (AETs, including drugs, ketogenic diet, vagal stimulators etc.)
- Record medical and surgical history.
- Record the types of seizures and the frequency of infantile spasms occurring ≤ 28 days of the Screening Visit based on parent/caregiver recollection.
- Record vital signs (seated or supine blood pressure [depending on patient age and ability], pulse rate, respiratory rate, and temperature measurements).
- Draw blood samples for hematology and chemistry.
 - o [Section 7.4](#) details the volume of samples to be drawn based on patient age.
- Perform a complete physical examination (see [Section 6.2.2](#)), including height, weight, and head circumference.
- Perform a complete neurological examination (see [Section 6.2.3](#)).
- Perform a minimum of 9-hr video-EEG that includes a full sleep-wake cycle.
- Completion of investigator CGI-S.
- Provide daily seizure diary to capture seizure activity (infantile spasms only) between visit 1 and visit 2, and train the caregiver to recognize and capture the infantile spasms.

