#### **5.2.3. Seizure Diary**

The seizure diary records the date, the number of spasms observed each day, and current dose of medications.

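### As written, no AE, SAE, diary or video-EEG endpoint records worsening of a pre-existing non-spasm seizure type, and a serious seizure event is not an SAE

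*Protocol*

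**What the plan says.** Protocol Section 6.2.6.1 takes seizures out of adverse-event reporting: "Seizures or worsening seizures are not considered AEs as they are considered part of the underlying disease". It then names two exceptions: "Injuries that occur as a result of a seizure, such as a broken nose, and new seizure types will be considered adverse events". Worsening of a type the infant already had is not among them.

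Protocol Section 6.2.6.4 builds the SAE definition on the AE definition: "A serious AE (SAE) is any AE that fulfills any of the following criteria". The hospital criterion, "Requires in-patient hospitalization or prolongation of existing hospitalization", therefore applies only to an event that is already an AE.

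The diary is a spasm record. At Screening (Protocol Section 7.1) the instruction is "Provide daily seizure diary to capture seizure activity (infantile spasms only) between visit 1 and visit 2", and footnote l of the Schedule of Events carries the same daily spasm record into the treatment periods. SAP Section 5.2.3 agrees: "The seizure diary records the date, the number of spasms observed each day, and current dose of medications". Protocol Section 8.4.3 has each video EEG read for the number of spasms and the presence of hypsarrhythmia. SAP Section 5.2.1 adds epileptic encephalopathy but no other seizure type.

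**The concern.** Exempting disease events from AE reporting is reasonable when an efficacy instrument counts them. For spasms, the diary and the central video-EEG reading largely do that. For any other seizure type the exemption applies just as fully, and nothing takes its place.

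Safety and tolerability is a stated secondary objective, assessed by comparing add-on CBD with add-on placebo. Protocol Section 8.4.4.1 limits AE summaries to TEAEs. If one arm had more aggravation of other seizures, those tables would not show it, and the SAE tables would not show the admissions. The safety comparison could then look more favourable to CBD than the infants' actual course.

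**Working it through.** The point rests on no sample-size, power or event figure, so there is nothing to reproduce. The check is to follow one event through every route in the documents: an infant enters with spasms and a second seizure type, and the second type worsens on treatment, with or without admission.

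**Can such an infant enrol?** Yes under the Protocol. No criterion in Sections 3.2.1 or 3.2.2 excludes other seizure types. Section 7.1 asks for the types of seizures at Screening, so more than one is foreseen. SAP Section 9.2 lists neonatal encephalopathy with seizures among the developmental risk factors.

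**Direct routes**
- AE (6.2.6.1): no. It is a worsening seizure, and neither an injury nor a new type.
- SAE (6.2.6.4): no, even with admission, because it is not an AE. The 24-hour SAE form in Section 6.2.6.7 is then not triggered.
- TEAE and SAE tables (8.4.4.1): no, for the same reason.
- Diary (Protocol 7.1 and footnote l; SAP 5.2.3): no. It counts spasms.
- Video-EEG endpoints (Protocol 8.4.3; SAP 5.2.1): no. They cover spasms and the EEG pattern.
- Relapse (8.1.2): no. It applies to complete responders and starts from a parent's report of relapse.
- Baseline comparison: no. Seizure types are recorded at Screening, with no planned on-treatment count of non-spasm seizures to set against them.

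**Indirect routes**
- CGI-I (8.1.2): possible but non-specific, as one global score. The Protocol schedules it at Visit 6 or Early Withdrawal only, so Extended Treatment completers have none after Day 15. SAP Section 4.3 lists it at Weeks 6, 10 and 13, and the two documents differ.
- Neurological examination and concomitant medications (8.1.3): a trace at most.
- AET review from Visit 6 onward, and withdrawal reasons (8.4.1.1): a trace at most.

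None of the indirect routes names the event or counts it.

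**Consequence for classification.** An infant whose spasms and hypsarrhythmia resolve while another seizure type worsens meets the Table 2 definition of complete response, enters the 75-day Extended Treatment Period, and has no seizure TEAE.

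**Spasms.** Ordinary worsening of spasms is measured by the diary and the Day 14 to 15 video EEG. A spasm event that meets a seriousness criterion is still not an SAE, because the exclusion covers all seizures. The Schedule of Events also shows no seizure diary in the 30-day follow-up, where the call collects AEs, AETs and concomitant medications. A serious spasm event after drug withdrawal can thus fall outside both systems.

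**The case against.** The best defence is that the exclusion is deliberate. Disease events are measured as efficacy, and injuries and new seizure types remain AEs. This stands for routine spasm counts, which should stay exempt. It does not stand for non-spasm types, which no efficacy instrument counts, or for serious events.

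A reader might infer that the harm is captured by no endpoint at all. The documents do not support that: the CGI-I is a secondary endpoint, and examination, medication, AET and withdrawal data can reflect the event. New AETs are also prohibited (4.7.2), so adding one to treat an aggravation would appear as a listed deviation. Nor can one say that the DSMC could not see it. Section 6.2.6.10 allows the committee access to clinical data, and its charter and the EEG Charter are not in the documents.

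A reader might also take the Protocol's background as evidence that CBD aggravates seizures here. In Section 1.2.1, "Tremors and convulsions occurred at >150 mg/kg" refers to a single intravenous dose in monkeys. The same section reports a 90-day oral monkey study at 30 to 300 mg/kg/day without clinical signs. Section 1.2.2 says that CBD given with other antiseizure drugs "increased or reduced their anticonvulsant activity, indicating that synergism or antagonism with cannabidiol was drug specific", but that is in adult rats. Its named examples, phenytoin and carbamazepine, are disallowed in this trial, and vigabatrin is not mentioned. The point needs no such evidence: a safety comparison should be able to detect this harm whether or not it is expected.

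Section 6.2.6.1 also lists worsening of a concomitant illness as a possible AE. A site might report a second seizure type under that line, but the specific sentence assigns seizures to the underlying disease, so this is at most a source of uneven reporting.

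**Conclusion.** The gap is real and should be closed. If the Protocol is followed exactly, worsening of a pre-existing non-spasm seizure type reaches no AE, SAE, diary or video-EEG endpoint, and a serious seizure event is not an SAE unless it falls under the two exceptions. Only non-specific traces remain. The primary efficacy comparison is not affected; the weakness lies in the comparison of TEAEs and SAEs by arm.

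Its size cannot be derived. The documents give no share of infants with a second seizure type, and multiplying an assumed share by 190 would count infants at risk, not events. SAP Section 9.3.2 says that patients with prior antiepileptic drugs are excluded, which might reduce the share, but neither document's exclusion list contains that general rule.

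Nor does the gap span all 190 infants for 90 days, as a reader might infer. It concerns infants with a second seizure type (and, for the SAE part, those with a serious seizure event), and only complete responders continue to Day 90. At the response rates assumed in Protocol Section 8.2, that is 130 × 0.60 + 60 × 0.40 = 78 + 24 = 102 infants. The other 190 − 102 = 88 would leave after the Initial Treatment Period, apart from the wait for the central reading and any taper.

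The conclusion assumes that the AE and SAE definitions are applied as written and that no unseen charter or form adds a record of other seizures.

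**What to change.** Amend Protocol Section 6.2.6.1 as follows:
- Spasm counts recorded in the diary stay exempt from AE reporting.
- Any seizure event, spasms included, that meets a seriousness criterion in Section 6.2.6.4 is reported as an SAE.
- Worsening of a non-spasm seizure type present at baseline is recorded as an AE.

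In the SAP, tabulate the last two by arm as seizure-related TEAEs, using the seizure types recorded at Screening to decide what counts as pre-existing.

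This changes recording, not clinical management, and uses the existing AE and SAE forms. The cost is a short amendment and some additional SAE reports that reflect the underlying disease; because allocation is randomised, the two arms can still be compared on them.

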6.2.6.2. Classification of Adverse Events

Adverse events are to be recorded on the AE page of the patient's case report form (CRF). Severity will be graded according to the following definitions:

- Mild: The patient experiences awareness of symptoms but these are easily tolerated or managed without specific treatment.
- Moderate: The patient experiences discomfort enough to cause interference with usual activity, and/or the condition requires specific treatment.
- Severe: The patient is incapacitated with inability to work or do usual activity, and/or the event requires significant treatment measures.

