3.2.1. Inclusion Criteria

All patients must satisfy the following criteria to be considered for study participation:

1. Parent(s)/caregiver(s) fully comprehend and sign the informed consent form, understand all study procedures, and can communicate satisfactorily with the investigator and study coordinator, in accordance with applicable laws, regulations, and local requirements.
2. Male or female between 1 months to 24 months of age (inclusive) at time of consent.
3. Clinical diagnosis of infantile spasms, confirmed by video-EEG analysis (including at least one cluster of electroclinical spasms [≥ 3 in any 10-minute epoch]) and hypsarrhythmia) obtained during the Screening Period and read by a central reader.
4. General good health (defined as the absence of any clinically relevant abnormalities as determined by the investigator) based on physical and neurological examinations, medical history and clinical laboratory values completed during the Screening Visit (Visit 1).
5. In the opinion of the investigator, the parent(s)/caregiver(s) is (are) willing and able to comply with the study procedures and visit schedules.

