3.5. Stopping Rules

The Investigator reserves the right to terminate the study in the interest of patient safety and welfare. The Sponsor reserves the right to terminate the study at any time for administrative reasons. Patients will also be discontinued when their liver enzymes and serum bilirubin reach:

- ALT or AST > 8 x ULN.
- ALT or AST > 5 x ULN for more than 2 weeks.
- ALT or AST > 3 x ULN and (TBL>2 x ULN or INR>1.5).
- ALT or AST > 3 x ULN with appearance of fatigue, nausea, vomiting, right upper quadrant pain or tenderness, fever, rash, and/or eosinophilia (> 5%).

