## **11. SAFETY AND TOLERABILITY**

### **11.1. Overall Summary of Tolerability**

The secondary objective of the study is to evaluate the safety and tolerability of Cannabidiol Oral Solution as adjunctive therapy with either vigabatrin or ACTH as initial therapy in treating patients with Infantile Spasms. This objective will be met by assessment of the following:

- Treatment-emergent AEs (TEAEs) and SAEs graded according to the Medical Dictionary for Regulatory Activities (MedDRA version 19.0 or above). These will be captured at every patient visit to the study center.
- Liver function tests.
- Complete blood counts.
- Concomitant medications
- Vital signs (temperature, blood pressure, pulse rate, and respiratory rate).
- Physical and neurological examinations.

Collection and monitoring of these data are detailed in [Sections 6.2.1 through 6.2.5 of the protocol](#).

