#### **11.2.1. Summaries of Adverse Event Incidence Rates for All Subjects**

Overall summary of TEAE's will be summarized by any TEAE, treatment-related TEAE, treatment-related and severe TEAE, TEAE leading to study drug discontinuation, any serious TEAE, any serious and treatment related TEAE and TEAE resulting in death. Summaries of AEs will include incidence of TEAEs and treatment-related TEAEs by MedDRA preferred term (PT) and system organ class (SOC). The TEAEs will also be summarized by severity, PT, and SOC. Subjects reporting more than one TEAE are counted once in each category at the maximum severity.

AEs with a start date during the study will be summarized. Listings of all AEs, AEs leading to discontinuation of the study, SAEs, and deaths, if any, will be provided.

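### The only AE severity scale has no laboratory-based or infant-specific criteria, so the severity tables cannot reflect the size of a symptom-free liver-enzyme rise

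*Protocol*

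**What the plan says.** Protocol 6.2.6.2 defines three grades. The lowest reads "Mild: The patient experiences awareness of symptoms but these are easily tolerated or managed without specific treatment". The middle grade calls for discomfort that gets in the way of what the patient normally does, or for an event that has to be specifically treated. The top grade reads "Severe: The patient is incapacitated with inability to work or do usual activity, and/or the event requires significant treatment measures".

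The patients are infants and toddlers: "Male or female between 1 months to 24 months of age (inclusive) at time of consent" (protocol 3.2.1). In defining an AE, protocol 6.2.6.1 says of a drug effect that "it could be an abnormal laboratory value", if the investigator considers it clinically important. Protocol 3.5 lists liver criteria at which patients are discontinued; the first is "ALT or AST > 8 x ULN", with no symptom condition attached.

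Severity is then reported. Protocol 8.4.4.1 plans AE summaries by severity. SAP 11.2.1 states "The TEAEs will also be summarized by severity, PT, and SOC", counts each patient at maximum severity, and gives events that are both treatment-related and severe their own line. SAP 11.1 describes TEAEs and SAEs as "graded according to the Medical Dictionary for Regulatory Activities (MedDRA version 19.0 or above", but neither that section nor any other in the SAP sets out severity grades.

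**The concern.** Safety and tolerability are a secondary objective, and protocol 8.1.3 names liver enzymes and serum bilirubin among the safety endpoints. Liver tests are also the only laboratory measure with a stopping rule. A reader of the study report will look to the severity tables to judge how bad the liver events were in each arm.

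The scale was written for patients who notice symptoms and go to work. It never asks how abnormal a laboratory value is. If the largest enzyme rises are graded without regard to size, the severity tables can look reassuring when the laboratory data do not. With about 35 sites planned (SAP technical summary), each site would also have to improvise a grade for an event that the text does not cover.

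**Working it through.** No arithmetic applies, and the plan gives no figure to reproduce. The check sets one event against each clause of the scale, then looks for any other planned output that would show its size.

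**Test event.** ALT above 8 x ULN, recorded as an AE; no symptoms; usual activity unaffected; no treatment given for it; study drug stopped under protocol 3.5.

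| Grade (protocol 6.2.6.2) | What the definition needs | Test event |
|---|---|---|
| Mild | Awareness of symptoms that are easily tolerated or need no specific treatment | Not met: there are no symptoms |
| Moderate | Discomfort that interferes with usual activity, and/or specific treatment | Not met: neither is present |
| Severe | Incapacity for work or usual activity, and/or significant treatment measures | Not met, unless stopping the drug counts as such a measure |

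On the last cell, protocol 6.2.6.5 records discontinuation as an action taken, in a separate field, and 6.2.6.2 does not say whether it counts towards severity. Read literally, the event fits no grade. Mild is the nearest default because nothing in the other two definitions is triggered. The result is the same at 3, 5 or 8 x ULN, because size is not an input.

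**Is there another scale?** No. SAP 11.1 refers to MedDRA, which protocol 8.4.4.1 uses to classify AEs and the protocol synopsis ties to system organ class and preferred term. The SAP gives markedly abnormal criteria for vital signs (11.6.1) but none for laboratory values.

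**Would the size show elsewhere?**

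- *Discontinuation summaries.* A rise that forces a stop and is recorded as an AE appears among TEAEs leading to discontinuation (protocol 8.4.4.1, SAP 11.2.1). That shows that it occurred, not how large it was.
- *Rises that force no stop.* Take a symptom-free rise between 5 and 8 x ULN lasting less than two weeks, with normal bilirubin and INR and no eosinophilia. It meets none of the four criteria in protocol 3.5, so it need not reach the discontinuation table, and it has no laboratory route to Severe.
- *Shift tables.* SAP 11.5 and the protocol synopsis define shifts by the normal range. A value just above ULN and one above 8 x ULN fall in the same cell.
- *Descriptive statistics and listings.* These include the maximum (SAP 10.1) and the individual values. They are the only planned outputs that carry the size, and they do not count patients by how far they exceeded ULN.

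**The case against.** The strongest reply is that the event is not hidden. It would be counted among discontinuations, it could be reported as an SAE under the medically significant criterion in protocol 6.2.6.4 whatever its severity grade, it would be in the laboratory listings, and a data monitoring committee reviews safety. All safety analyses are descriptive, so no test is distorted. This stands, and it limits the consequence: harm would be understated in the severity tables, not lost from the report. It does not cover rises that force no stop, and it does not supply a summary by size.

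Three stronger readings are tempting, and the documents do not support them.

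- A reader might infer that such an event can only be graded Mild. Mild itself needs awareness of symptoms, so the literal result is no grade at all. An investigator could also argue for Severe by treating the forced stop and taper as a significant treatment measure.
- A reader might infer that severity is self-reported by infants. Protocol 6.2.6.7 has the investigator rate intensity, and 7.2.1.5 has the parent or caregiver note adverse events. The wording is symptom-based, not self-reported.
- A reader might infer that the work criterion makes Severe unusable in infants. The definition offers usual activity as an alternative, and that can be judged in an infant.

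Nor does the point cover all liver toxicity. The fourth criterion in protocol 3.5 pairs an enzyme rise with clinical signs or eosinophilia, and the existing scale can grade most of those signs.

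**Conclusion.** The point holds for symptom-free, untreated rises in ALT or AST. The only severity scale cannot express their size, the event meets none of the three definitions, and Mild is the probable default. The severity tables and the line for treatment-related severe events would therefore tend to understate liver-enzyme harm.

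This rests on two assumptions: that investigators record such values as AEs, and that most would settle on Mild when no definition fits. Neither can be verified from the documents. No number of affected patients can be given, because the sample size and safety analysis sections assume no rate of enzyme rises.

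The change is worth making. It affects how a named safety endpoint is reported; it does not touch the primary endpoint or any safety decision rule.

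**What to change.** For reporting only, with the stopping rules left as they are:

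1. **Protocol 6.2.6.2.** State how ALT, AST and bilirubin AEs map to Mild, Moderate and Severe, using the multiples of ULN already in 3.5. For ALT and AST these are 3, 5 and 8, enough cut points to separate three grades. For bilirubin there is only one, 2 x ULN, which separates two. The sponsor's medical staff should choose the mapping; it must never fall as the value rises, and it should be fixed before unblinding. Limit it to liver tests, since 3.5 gives no thresholds for haematology or other chemistry. Replace the *awareness* and *work* wording with signs that an investigator or caregiver can observe in an infant, such as feeding, alertness and usual play.
2. **SAP 11.5.** Add a table by arm, in the Safety Population, of the number and percent of patients whose maximum post-baseline ALT or AST is > 3, > 5 and > 8 x ULN, and of those with ALT or AST > 3 x ULN plus bilirubin > 2 x ULN.
3. **SAP 11.1.** Say that AEs are coded using MedDRA and graded per protocol 6.2.6.2.

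The cost is protocol, CRF-guideline and SAP wording plus one table. No new data are needed, because protocol 6.2.5.2 already collects ALT, AST and bilirubin. The downside is that some laboratory events will be graded higher than under the present scale.
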